3.11 Derived data

The derived data are variables which are calculated from the raw data in the eCRF and not included in the database.

The following derived data will be calculated and included in the listings:

(1) Age

Subject age (years) will be derived as (screening year – birth year).

(2) BMI

BMI (kg/m^2) will be derived as $\text{Weight}(\text{kg})/[\text{Height}(\text{cm})/100]^2$.

(3) Changes from Baseline

Changes from Baseline will be calculated as a difference from Baseline (e.g. assessment at the visit – assessment at Baseline).

(4) Adverse event duration

The AE duration = AE end date - AE start date + 1. If the start and end dates of the adverse event are identical then “ <1 ” day will be presented, otherwise, it will be calculated as (end date - start date)+1 and presented in days. If the recorded end date is CONT. (for continuing), the end date will be listed as “ongoing” and the duration will be approximated as “ $\geq(\text{last attended visit date} - \text{start date})+1$ ” day(s). If the start date or the end date are partial the duration will be presented as a superior inequality “ $\geq xx$ ” day(s) [i.e.: ≥ 2 where start date=31JAN2004 and end date=FEB2004 or start date=JAN2004 and end date=01FEB2004].

(5) Concomitant therapy duration

The duration of concomitant treatments/physiotherapy etc. will be calculated as (end date - start date) +1. If the recorded end date is CONT. (for continuing) then the end date will be listed as “ongoing” and the duration will be approximated as “ $\geq(\text{last attended visit date} - \text{start date})+1$ ” day(s). If the start date or the end date are partial, the duration will be presented as an inequality “ $\geq xx$ ” day(s) [i.e.: ≥ 2 where start date=31JAN2004 and end date=FEB2004 or start date=JAN2004 and end date=01FEB2004] but if both are partial or one is missing the duration will not be presented.

(6) Study day

Study day will be defined as ‘-1’ for the day prior to first study drug administration and as ‘1’ for the day of first study drug administration (i.e. day 0 does not exist).

(7) Study Baseline

Baseline is defined as the last value, or the derived value specified for the parameter, available prior to the first study IMP treatment administration (i.e. prior to the DB period). Baseline for the active dysport cycle analysis will be the same as Baseline for the DB period, i.e., Baseline of the first study cycle.

(8) Treatment cycle day

For events within the i^{th} cycle, the treatment cycle day = date of event - (date of (i)th injection) +1.

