### 3.7.3 *Retreatment Criteria (Stage 1 and Stage 2)*

From Week 12 onwards (Stages 1 and 2), need for retreatment will be assessed at each visit. All subjects willing to continue in the study will be offered to receive Dysport (under an open-label design).

Retreatment with Dysport will only be initiated if all of the following criteria are fulfilled (retreatment criteria):

- At least 12 weeks have elapsed since the last treatment received.
- Based on investigator's judgement, this is in the best interest of the subject.
- Subject is willing to be retreated.
- The subject has not experienced any unacceptable AE as judged by the investigator.
- Negative urine pregnancy test.
- Negative drug screen test for illicit drugs.

Details on dose administration for Stage 1 are provided in Sections [3.7.2.1](#) and for Stage 2 in Section [3.7.2.2](#).

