### Stage 2:

The study sample size required to have at least 80% power to detect a 2-point improvement for an experimental drug arm relative to placebo on mean change from baseline to Week 6 in the vaginal dilator induced pain as reported on a numeric pain rating scale (using the DMTS) using a one-sided 0.10 level test (not corrected for multiplicity) is 21 evaluable subjects per arm (i.e. a total of 63 subjects). The following assumptions were used for the power statement:

- Expected outcome on the mean change from baseline to Week 6 in the vaginal dilator induced pain as reported on a numeric pain rating scale in the placebo group = 2-point decrease (reference approximated by VAS per speculum in Bornstein, 2010 [26])
- Expected outcome on the mean change from baseline to Week 6 in the vaginal dilator induced pain as reported on a numeric pain rating scale in a Dysport treated group = 4-point decrease
- Expected common standard deviation of the mean change from baseline to Week 6 in the vaginal dilator induced pain as reported on a numeric pain rating scale = 3-points (approximated per VAS data in Table 2 in Davis 2013 [27]).

Subject who discontinue prior to Week 6 for reasons unrelated to safety will be replaced at the discretion of the investigator and sponsor.

At the end of Stage 2, if the true DLE rate is 6% or greater, there is at least 80% probability to observe at least 1 DLE in 29 subjects (8 in Stage 1 and 21 in Stage 2). Therefore, if there are no observed DLEs in both Stage 1 and Stage 2 at a dose level, then there is good confidence that the true DLE rate is no more than 6%. If the dose chosen in Stage 2 has been tested on two cohorts (PWD1 and PWD2) in Stage 1, at the end of Stage 2, if the true DLE rate is 5% or greater, there is at least 80% probability to observe at least one DLE in 37 subjects (16 in Stage 1 and 21 in Stage 2). Therefore, if there are no observed DLEs in both Stage 1 and Stage 2 at a dose level, then there is good confidence that the true DLE rate is no more than 5%. If it is reasonable to assume that the relationship between toxicity and dose level is monotonic non-decreasing, then we may pool dose levels to obtain a higher degree of confidence for the lower dose level.

Following the review of data available from Stage 1, the sample size may be formally recalculated for Stage 2 after the intermediate analysis.

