No control of the overall type I error rate is planned as only exploratory descriptive statistics are planned.

2 **SUBJECT POPULATIONS (ANALYSIS SETS)**

Screened population

The screened population is all subjects screened (i.e. who signed the informed consent).

Randomized population

Randomized population is all subjects randomized (i.e. who were randomly allocated to a treatment group).

modified Intent-To-Treat population

The modified Intent-to-Treat (mITT) population is all randomized subjects who received at least one IMP administration and had data for the vaginal dilator induced pain as reported on an 11-point NRS [using the Dilator Maximum Tested Size (DMTS) reported at Baseline] at Baseline and Cycle 1-Week 6 visit (i.e. at least one pain score for one dilator size, which enables an imputed pain score of 10 at DMTS if needed).

The mITT population will be analyzed using subjects as randomized.

Active Treatment Population

The Active Treatment Population is all randomized subjects who received at least one dose of Dysport (including only partial administration) during the DB and/or OL period.

Safety

The safety population is all randomized subjects who received at least one dose of IMP administration (including only partial administration).

The safety population will be analyzed using subjects as treated (i.e. according to actual treatment received).

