3 STATISTICAL METHODS

3.1 Statistical analysis strategy

The statistical analyses will be performed in accordance with the ICH E9 guideline and will be based on the pooled data from the individual study sites, unless otherwise stated.

Medpace will perform the statistical analysis of the efficacy, safety, and antibodies data.

Overall, the analysis strategy is to evaluate safety and efficacy of Dysport compared to Placebo after single administration (DB period), and to evaluate efficacy and safety over repeated Dysport treatments, using analyses by Active Treatment Cycle.

Listings will be presented by subject for DB and OL periods together while the tables associated with the DB period will be separated from the tables assessing repeat treatment with Dysport.

Only descriptive statistics of Stage 1 data will be provided.

Double-Blind Period (Stage 1 Cycle 1) Analyses

For the analysis of the DB period, tables will be displayed using the following treatment group (DB treatment group) labels, in the following order:

- Placebo: placebo groups from all cohorts will be pooled, including for mVPAQ pain, mVPAQ life interference and mFSFI pain domain of cohort 1 despite the change in recall period and time of assessments (see protocol version 3.0).
- Dysport
 - Groups by dose (Dysport 100U, 300U, 400U, 500U, etc.)
 - All Dysport

[figure not shown]
Note: Cohort 1 (100U), 2 (300U), 3 (400U) and 5 (500U) included PVD2 subjects only. Cohort 4 (400U) and 6 (500U) included PVD1 subjects only.

Repeat treatment: Active Treatment Analyses

To assess efficacy and safety data over repeat treatments, data will be analysed using the Active Treatment Cycle approach as described in [Figure 1](#) below. These analyses will be performed on the Active Treatment population:

- for subjects treated with Dysport in the DB period, the first cycle in the DB period will be the first Active Treatment Cycle.
- for subjects treated with placebo in the DB period, the first cycle in the OL period will be the first Active Treatment Cycle.

[Figure 1](#) Active Treatment Cycle Analysis

Three types of summary tables will be produced:

- Summary by number of active treatment cycles: these tables will present the long-term efficacy and safety data with all doses combined, and will display subjects with at least 1 (2, 3 and 4) active treatment cycles.
- Summary by dose received at each active treatment cycle: to evaluate the safety of each dose at a given cycle.

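### In the active-cycle efficacy tables, placebo-first subjects are measured from before placebo, so any placebo-period change that persists is reported within a Dysport cycle

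*SAP*

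**What the plan says.** SAP section 3.11, item (7), sets Baseline as the last value before the first injection of any study product, placebo included, and carries it into the repeat-treatment analysis: "Baseline for the active dysport cycle analysis will be the same as Baseline for the DB period".

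SAP section 3.1 defines the cycles differently for the two arms. On one side, "for subjects treated with Dysport in the DB period, the first cycle in the DB period will be the first Active Treatment Cycle". On the other, "for subjects treated with placebo in the DB period, the first cycle in the OL period will be the first Active Treatment Cycle".

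Both groups enter the same tables. The Active Treatment Population (SAP section 2) is "all randomized subjects who received at least one dose of Dysport (including only partial administration) during the DB and/or OL period", and for the summaries by number of active cycles section 3.1 says that "these tables will present the long-term efficacy and safety data with all doses combined". SAP section 3.8 applies this layout to the efficacy endpoints.

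The interval before open-label Dysport comes from Protocol section 3.7.3, whose first retreatment criterion is "At least 12 weeks have elapsed since the last treatment received".

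Two provisions separate the randomised arms. SAP Table 1 requires a plot of dilator-pain change by randomised group over the double-blind and first open-label periods. SAP section 3.1 also says that a summary by randomised group may be produced for some efficacy analyses. No alternative baseline is specified.

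**The concern.** A column labelled active cycle 1 invites the reader to take its change from baseline as change on the first Dysport treatment. For Dysport-first subjects the reference value immediately precedes that treatment. For placebo-first subjects it precedes a placebo injection and at least 12 weeks of follow-up, so their active cycle 1 Week 6 visit falls at least 12 + 6 = 18 weeks after Day 1. One mean then combines two quantities: change since just before the first Dysport dose, and change since before placebo.

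Carry-over is plausible on the plan's own terms. The protocol expects pain to fall on placebo, and entry requires a score of at least 5 at Baseline (inclusion criterion 10a), which favours regression to the mean.

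The mix also shifts across the columns. Protocol section 3.8 caps treatments at four including the double-blind one, so placebo-first subjects can have at most three active cycles. They are present in cycle 1 and absent from cycle 4.

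At stake is how the repeat-treatment efficacy tables are read. These are descriptive; no test, error rate or sample size depends on them.

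**Working it through.** **Inputs**

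- Planned subjects in cohorts 1 to 6 (Protocol 11.2; SAP 1.3.5 and 3.1): five cohorts of 8 Dysport + 2 placebo, and Cohort 4 with 6 Dysport + 2 placebo. Dysport: 8 × 5 + 6 = 46. Placebo: 2 × 6 = 12. Total: 58.
- Placebo change (Protocol 11.2, Stage 2): "in the placebo group = 2-point decrease". The same list gives a 4-point decrease on Dysport and an SD of 3.
- Not in the documents, so varied: the number *m* of placebo-first subjects entering the open-label period, and the fraction *r* of their placebo change still present at the open-label visit.

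**The plan's own figure.** The 2-point placebo value belongs to the Stage 2 sample size. With a difference of 2, SD 3, one-sided 0.10 and 80% power, n = 2 × (1.2816 + 0.8416)² × 3²/2² = 20.3, rounded up to 21 per arm. This reproduces the stated 21 and is not in dispute.

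**Share of placebo-first subjects.** At active cycle 1: up to 12/58 = 20.7%. At active cycle 4: zero, because of the cap of four treatments.

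**Difference between the two references.** For a placebo-first subject, change from the study baseline equals change from the pre-Dysport value plus the retained placebo-period change, 2 × r. In the pooled mean the difference is 2 × r × m/(m + 46):

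| m | r = 0 | r = 25% | r = 50% | r = 100% |
|---|---|---|---|---|
| 12 | 0 | 0.10 | 0.21 | 0.41 |
| 9 | 0 | 0.08 | 0.16 | 0.33 |
| 6 | 0 | 0.06 | 0.12 | 0.23 |

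If 60% enter with full retention: 7.2/53.2 × 2 = 0.27. If the placebo change is 1 to 3 points instead of 2 (m = 12, full retention): 0.21 to 0.62. If subjects worsen on placebo, the sign reverses. Within placebo-first subjects alone, the difference is 2 × r, so 0 to 2 points.

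**Is the pooled mean too large?** Take the protocol's figures, full retention and additive effects. Dysport-first subjects change by −4. Placebo-first subjects change by −2 on placebo and a further −2 on Dysport.

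- Study baseline for all: (46 × −4 + 12 × −4)/58 = −4.00.
- Pre-Dysport reference for placebo-first subjects: (46 × −4 + 12 × −2)/58 = −3.59.

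Here the common baseline gives the same value in both groups, and replacing it produces a mixture. With no Dysport effect and every subject at −2, the corresponding figures are −2.00 and (46 × −2 + 12 × 0)/58 = −1.59.

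**Responder tables.** With mean −2, SD 3, full retention and a normal approximation, the chance that a placebo-first subject already meets the 2-point rule before any Dysport is Φ((−2 + 2)/3) = 50%.

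**The case against.** The strongest reply is that a single pre-treatment baseline is explicit, matches the protocol's endpoints, and measures total change consistently. The −4.00 against −3.59 example supports this. The protocol's Dysport figure itself includes any placebo response, so removing that response from one group only would make the groups less alike. This stands. A reader might infer that the cycle 1 mean is inflated; the documents do not show that, because 0.41 is the gap between two definitions.

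The same baseline also serves every active cycle, so a subject's offset cancels in any within-subject contrast between cycles. That stands too. It does not cover comparisons of column means, where the share of placebo-first subjects changes.

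Retention is unknown. The 2-point figure is a Week 6 planning value approximated from another pain measure, whereas the visits concerned are 18 weeks or more after Day 1. Under Protocol 3.7.3 retreatment also depends on the investigator's judgement, which may favour subjects whose pain has returned. Zero is therefore a legitimate end of the range.

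Some separation already exists, but the required part is one plot for one endpoint. The composite score, dilator number 6 pain, intercourse pain and PGI-S have no required equivalent.

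A reader might extend the point to laboratory values. The open-label schedule (Protocol Table 3) has laboratory tests only at the end-of-study or early-withdrawal visit, so there is no per-cycle laboratory series to distort.

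Finally, the study stopped before Stage 2, and the data review committee advised against using Stage 1 to assess efficacy (SAP 1.3.5). This limits the consequence, but the tables are still to be produced.

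**Conclusion.** The point holds as one of definition and presentation. For placebo-first subjects, the active cycle 1 efficacy change includes whatever placebo-period change persists, in either direction, and it is pooled with Dysport-first subjects without a required breakdown beyond one plot. With the protocol's 2-point placebo fall and all 12 planned placebo subjects entering, the pooled cycle 1 mean differs from the pre-Dysport reference by 0 to 0.41 points, and by 0.21 at 50% retention. This rests on planned cohort sizes and on assumed entry and retention.

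Two further inferences are not supported. The double-blind comparison with placebo is not affected: both arms there are measured from the same point before their first injection. Nor would re-baselining isolate a Dysport effect, because the active-cycle tables have no concurrent control and the Dysport-first changes also contain non-specific response.

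**What to change.** Keep the study baseline as the main reference and amend SAP sections 3.1, 3.8 and 3.11 as follows.

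- Make it mandatory to show the active cycle 1 efficacy change-from-baseline and responder tables by double-blind arm (placebo-first and Dysport-first).
- For placebo-first subjects, add change from the last value before the first Dysport injection on the continuous endpoints: dilator pain at the DMTS fixed at Baseline, composite score, dilator number 6 pain, intercourse pain and PGI-S.
- Do not re-baseline PGI-C or CGI, whose questions refer to the state before study treatment began (Protocol 7.4.2.4.2 and 7.4.3.2). Do not re-baseline the 30% and 50% responder endpoints either: without the entry floor of 5, a subject could have a low or zero denominator.

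The data are already scheduled. The dilator test is done at Week 12 and each additional visit, Cycle 2 Day 1 is normally the same day, and the test is repeated if more than two weeks have passed (Protocol 5.2.2.4, 5.2.2.5, 5.2.3.1; Table 2, footnote a). The cost is SAP wording and extra columns based on about 12 subjects, which will be imprecise and should be labelled as such.

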3.12 Rules and data formats

Data will be presented using an appropriate number of decimal places (i.e. the number of decimal places used does not imply undue precision). Raw data will be presented to the number of decimal places collected, and derived data will be presented to an appropriate number of decimal places. The appropriate number of decimal places will be determined by general practice, mathematical rationale or scientific rationale (e.g. age should be presented in whole numbers).

Mean, median, standard deviation and standard errors of the mean (SE) values will be reported to one decimal place greater than the raw/derived data that they summarize. Minimum and maximum values will be reported with the same precision as the raw data.

Percentages will be reported to one decimal place and 0% will not be presented. Percentages will be calculated using a denominator of all subjects in a specified population. The denominator will be specified in a footnote to the tables for clarification if necessary.

Percentiles (e.g., 25%, 75%) should be presented to one decimal place more than the raw/derived data.

Lower and upper confidence interval values should be presented to one decimal place more than the raw/derived data (i.e., to the same number of decimal places as the mean).

P-values will be reported to four decimal places (e.g.: $p=0.0037$), after rounding. P-values which are less than 0.0001 will be presented as ‘<0.0001’.

All values below or above a limit of detection (e.g. <0.1 or >100) will be listed as such.

All text fields must be left justified and numeric or numeric with some text specification (e.g.: not done, unknown, <4.5, ...) must be decimal justified. Dates will be presented in the format [ddmmmyyyy] and times in the format [hh:mm].

3.13 Pooling of Centres

A subgroup analysis on individual or groups of centres will not be performed.

3.14 Covariates and analysis of subgroups

The following statistical analyses by pain onset subtype (randomization stratification factor) will be done:

- Demographics and baseline characteristics will be summarized by pain onset subtype, in the mITT population.
- Descriptive statistics for the change from Baseline to Week 6 and Week 12 in the vaginal dilator induced pain as reported on an 11-point NRS (using the

DMTS reported at Baseline) will be provided by pain onset subtype (primary and secondary PVD) on the mITT population for DB period.

- Descriptive statistics for the change from Baseline to Week 6 and Week 12 in the dilator size that provokes maximum tolerated pain will be provided by pain onset subtype (primary and secondary PVD) on the mITT population for DB period.
- An overall adverse events summary will be done; TEAEs and SAEs will be described by SOC and PT for DB period (please refer to Section 3.9 for more details on the summary strategy).

3.15 COVID-19 impact

The e-CRF was amended in order to collect data related to COVID-19 impact. These will be summarized as described thereafter.

Disposition

To assess the impact of COVID-19 pandemic on the trial, the following summaries will be provided:

- Proportion of subjects impacted and withdrawn due to COVID-19 pandemic.
 - the reasons of discontinuation related to COVID-19 will be presented separately.
 - the number of subjects exposed as well as impacted or infected will also be presented.
- Number of subjects with visits impacted by COVID-19 with the corresponding reason.
 - the number of subjects per visit as well as the number of subjects with a missing visit per timepoint.
 - the number of visits impacted due to COVID-19 with the reasons will be presented to assess the impact of COVID-19.

Demographic and Baseline characteristics

Summary statistics will be provided for demographic and Baseline characteristics, by DB treatment group in subjects recruited (based on informed consent date) before and after (inclusive) the start of COVID-19 pandemic [i.e. 27-Jan-2020 based on date when the Public health emergency was declared by Health and Human Services] in order to identify a potential change in the general subject's characteristics.

Exposure

To assess the impact of COVID-19 pandemic on the trial, the time elapsed between injections will be described for injections done before and after the start of COVID-19 pandemic (27-Jan-2020), which will be presented by cycle and one subject will be counted once per cycle and period. Any cycle that ongoing on 27-Jan-2020 or after 27-Jan-2020 will be considered as cycle after the start of COVID-19 pandemic.

